5.5. Other Effectiveness Endpoints Analysis

The other effectiveness endpoints listed in [Table 5-4](#) will be summarized descriptively based on the observed data.

The analyses of CP will be performed for the mITT population at Baseline and Month 1. The analyses of TP will be performed for the VT population at Baseline and Months 1, 2, 4, and 6.

JUVÉDERM VOLITE™ XC

The analyses of RP will be performed for the VRT population at Baseline and Months 1 and 4 post the repeat treatment.

The composite responder status is defined based on ACSS and FACE-Q Satisfaction with Skin Questionnaire overall converted score. A participant is counted as a composite responder if both criteria listed below are met:

- ACSS criterion: A participant with at least 1-point reduction from baseline in ACSS on both cheeks will be considered as an ACSS responder
- FACE-Q satisfaction with skin responder: A participant with change from baseline in FACE-Q overall converted score \geq half of standard deviation of FACE-Q overall converted score at baseline ([Pusic 2013](#))

Table 5-4 **Other Effectiveness Analyses**

Endpoint	Description	Analysis Period	Methodology
ACSS responder status as assessed by EI	Number (%) of responders by treatment group	TP, RP	Frequency counts and percentages
Raw value and change from baseline in ACSS	Summary by treatment group	CP, TP, RP	Continuous descriptive statistics
Raw value and change from baseline in FACE-Q Satisfaction with Skin questionnaire overall converted score	Summary by treatment group	TP, RP	Continuous descriptive statistics
Item score of FACE-Q Satisfaction with Skin questionnaire and aggregated categories of “satisfied” and “dissatisfied”	Number (%) of each response category by treatment for each of 12 individual items	CP, TP, RP	Frequency counts and percentages
AFLS responder status as assessed by EI	Number (%) of responders by treatment group	TP, RP	Frequency counts and percentages
Raw value and change from baseline in AFLS	Summary by treatment group	CP, TP, RP	Continuous descriptive statistics
Raw value and change from baseline in FACE-Q Appraisal of Lines questionnaire overall converted score (see Section 6.5.3 and Section 6.5.4)	Summary by treatment group	CP, TP, RP	Continuous descriptive statistics
Item score of FACE-Q Appraisal of Lines questionnaire and aggregated categories of “satisfied” and “dissatisfied”	Number (%) of each response category by treatment for each of 12 individual items	CP, TP, RP	Frequency counts and percentages
Participant assessment of the natural look of the cheek skin on an 11-point scale ranging from 0 (unnatural looking) to 10 (natural looking)	Summary by treatment group	TP, RP	Frequency counts, percentages and Continuous descriptive statistics
Participant assessment of the natural feel of the cheek skin on an 11-point scale ranging from 0 (unnatural feeling) to 10 (natural feeling)	Summary by treatment group	TP, RP	Frequency counts, percentages and Continuous descriptive statistics
GAIS responder status defined as “improved” or “much improved” as assessed by participant (Table 5-5)	Number (%) of responders by treatment group	TP, RP	Frequency counts and percentages
GAIS raw score as assessed by participant	Number (%) of each response category by treatment group	TP, RP	Frequency counts and percentages
Raw value and change from baseline in skin hydration; the median of multiple assessments per cheek per e-CRF visit will be calculated and the average of the medians of both cheeks will be used for the analysis	Summary by treatment group	CP, TP, RP	Continuous descriptive statistics
Composite responder status on ACSS and FACE-Q satisfaction with skin questionnaire	Number (%) of responders by treatment	CP, TP, RP	Frequency counts and percentages

Endpoint	Description	Analysis Period	Methodology
overall score	group		

Table 5-5 Global Aesthetic Improvement Scale

Score	Grade	Description
2	Much Improved	Marked improvement in appearance
1	Improved	Improvement in appearance, but a touch-up or retreatment is indicated
0	No Change	The appearance is essentially the same as the original condition
-1	Worse	The appearance is worse than the original condition
-2	Much Worse	The appearance is much worse than the original condition

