10.3.1.1 Effectiveness Endpoints

Primary effectiveness endpoint:

- ACSR responder status at Month 1

Secondary effectiveness endpoints:

- Change from baseline to Month 1 in subject responses to FACE-Q Satisfaction with Skin questionnaire
- AFLS responder status at Month 1 (for subjects with baseline AFLS score of 2 on both cheeks or 3 on both cheeks)

Other effectiveness endpoints:

- Primary and secondary endpoints at other applicable timepoints

- Change from baseline in subject responses to FACE-Q Appraisal of Lines-Overall questionnaire
- Subject assessment of the natural look of the cheek skin on an 11-point scale ranging from 0 (unnatural looking) to 10 (natural looking)
- Subject assessment of the natural feel of the cheek skin on an 11-point scale ranging from 0 (unnatural feeling) to 10 (natural feeling)
- Subject assessment of the global aesthetic improvement of the cheek skin on the 5-point GAIS
- Change from baseline in cheek skin hydration measurements obtained via the MoistureMeter® D instrument

Exploratory effectiveness endpoint:

- Composite responder status responder status on ACSS and FACE-Q Satisfaction with Skin questionnaire

Effectiveness analyses other than those for primary and secondary endpoints will be defined in the SAP.

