Among the 210 participants randomized, at least 135 participants are expected to have a baseline AFLS score of 2 on both cheeks or 3 on both cheeks. The number of participants with baseline AFLS score of 0, 1, or 4 on either cheek, or 2 on one cheek and 3 on the other cheek is not expected to exceed 75. Assuming at least 65% of participants will have baseline AFLS score of 2 on both cheeks or 3 on both cheeks, 72 participants in treatment group and 36 participants in control group will provide 94.4% power to detect a difference of at least 35% in the responder rates on AFLS between the treatment groups, based on a 2-sided Fisher's exact test at the 5% level. The treatment group is assumed to have at least an 80% responder rate at Month 1, and the control group is assumed to have at most a 45% responder rate. The assumptions of responder rates are estimated from Allergan Study V12-001.

The sample size calculations used an inequality test for 2 proportions to demonstrate that the treatment group is superior to the control group.

Assuming 119 participants from the treatment group and 28 participants from the control group will be treated, a total of 147 treated participants will provide 95% power to detect an AE related to treatment with an incidence rate of 2% in the population using a 1-sided exact binomial test at the 2.5% level.

The commercial software, PASS (2008, Version 8.0.13), was used for the power calculations.

4. Populations for Analysis

The analysis populations will consist of participants as defined in Table 4-1.

Table 4-1 Analysis Populations

Population	Definition	Study Treatment Assignment
mITT	All randomized participants who have baseline assessment on the ACSS scale for both cheeks, and are not in the Fitzpatrick V/VI safety cohort (see the definition below)	As randomized
Observed Primary Endpoint	All mITT participants who have Month 1 assessment on the ACSS scale for both cheeks	As randomized
Safety	All participants who are randomized and received study intervention (VOLITE or no treatment)	As treated
VOLITE Treated (VT)	Participants randomized and received VOLITE treatment at the beginning of the Control Period, or Participants randomized and received optional VOLITE treatment after the Control Period.	As treated
VOLITE Repeat Treatment (VRT)	Participants in the VT who received VOLITE repeat treatment	As treated

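### AFLS responder rates in the treated and repeat-treatment periods lack the baseline 2/2 or 3/3 restriction, so they are not comparable with the Month 1 secondary result

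*SAP*

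**What the plan says.** Protocol 10.3.1.1 gives the second secondary endpoint as "AFLS responder status at Month 1 (for subjects with baseline AFLS score of 2 on both cheeks or 3 on both cheeks", so the baseline condition is part of the endpoint. Protocol 10.3.1.3 repeats it for the analysis. The same list in 10.3.1.1 then places "Primary and secondary endpoints at other applicable timepoints" among the other effectiveness endpoints.

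The SAP treats the periods differently:

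- **Control period (CP).** SAP 5.4.2 compares Month 1 AFLS responders in the mITT population limited to baseline 2 on both cheeks or 3 on both (2/2 or 3/3 below).
- **Treated period (TP).** SAP 5.5 states: "The analyses of TP will be performed for the VT population at Baseline and Months 1, 2, 4, and 6".
- **Repeat-treatment period (RP).** SAP 5.5 states: "The analyses of RP will be performed for the VRT population at Baseline and Months 1 and 4 post the repeat treatment".

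Table 5-4 lists "AFLS responder status as assessed by EI" for TP and RP as counts and percentages, with no baseline condition. Table 4-1 defines VT as "Participants randomized and received VOLITE treatment at the beginning of the Control Period", plus controls who took the optional treatment afterwards, and VRT as "Participants in the VT who received VOLITE repeat treatment". Neither definition mentions AFLS. The responder definition in SAP 5.4.1 asks for a 1-point improvement on both cheeks and sets no baseline condition.

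Protocol 6.1 has no AFLS entry criterion, and SAP Section 3 foresees participants outside the restricted set. It says "The number of participants with baseline AFLS score of 0, 1, or 4 on either cheek", or with 2 on one side and 3 on the other, should not exceed 75 of the 210 randomized.

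**The concern.** AFLS 0 means no fine lines. A participant who starts at 0 on either cheek has no room to improve there and so can never be a both-cheeks responder. The ACSS row of the same table does not have this problem outside the Fitzpatrick V/VI safety cohort, because entry requires ACSS 2 on both cheeks or 3 on both. AFLS has no such protection.

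Two things follow for a reader of the study report. First, in the treatment group CP and TP both start at initial treatment (SAP Table 5-1), so the Month 1 visit would yield one AFLS responder rate on the restricted set and another on all treated participants. Second, anyone who sets the Month 1 secondary result against the Month 2, 4 or 6 rates, or against the repeat-treatment rates, would be comparing different populations. A lower later rate could then reflect the change of denominator as well as loss of effect.

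**Working it through.** **1. Reproduce the plan's own figure.** Inputs from SAP Section 3: 72 treated and 36 control participants with baseline 2/2 or 3/3, responder rates of 80% and 45%, two-sided Fisher's exact test at 5%. Enumerating both binomial distributions gives power of 94.40%, against 94.4% stated. The 108 participants agree with 135 × 0.80 = 108 after 20% attrition. This power belongs to the restricted CP comparison, which the SAP keeps, so the present point does not touch it.

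**2. How many participants the missing condition could bring in.** The ceiling outside 2/2 or 3/3 is 75/210 = 35.7%. Applied in proportion to the 147 expected treated participants, that is 147 × 75/210 = 52.5. The restricted set would be about 147 × 135/210 = 94.5, or 147 × 0.65 = 95.6 using the plan's 65%.

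**3. Who among them is a certain failure.** Only those with a 0 on at least one cheek. Participants at 1, at 4, or at 2 with 3 can still improve by a point on both cheeks.

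**4. Effect on the rate.** Let q be the share of the 75 who have a 0 on at least one cheek. The documents do not give q. Assume that everyone without a 0 responds at the plan's 80%, and that the ceiling of 75 is reached. Then:

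unrestricted rate = 0.80 × (1 − 0.357 × q)

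| q | Share of all participants with a 0 | Unrestricted rate | Difference from 80% |
|---|---|---|---|
| 0 | 0% | 80.0% | 0 points |
| 10% | 3.6% | 77.1% | 2.9 points |
| 25% | 8.9% | 72.9% | 7.1 points |
| 50% | 17.9% | 65.7% | 14.3 points |
| 100% | 35.7% | 51.4% | 28.6 points |

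**5. What this does across visits.** If z is the share with a 0 among those assessed, each TP rate is multiplied by (1 − z). Participants with a baseline 0 are failures at Months 1, 2, 4 and 6 alike. Apart from missing visits, the factor is therefore the same throughout TP, and the ratio of a later rate to TP Month 1 is unchanged. The distortion appears between CP Month 1 and any TP rate. It can also appear between TP and RP, since VRT is the subset who took repeat treatment and z may differ there.

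**The case against.** The strongest reply has four parts.

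- **The conflict with the protocol is partly inferred.** The restriction is written against Month 1. Protocol 4.1, to which SAP 1.1 refers for endpoints, lists AFLS responder status without it, and 10.3.1.1 leaves analyses beyond primary and secondary to the SAP. That is fair. Carrying the secondary endpoint to other timepoints with its restriction is the natural reading rather than an explicit rule. The SAP, however, neither states nor justifies a wider AFLS population.
- **It is an omission in descriptive tables.** The SAP does not say that it removes the restriction, and table specifications sit in a separate document that is not available here. This stands, and the final tables may be filtered correctly. As the SAP is written, though, a programmer would include every VT or VRT participant with observed data.
- **Durability does not rest on these rates.** A reader might infer that they are the sole evidence on how long the fine-line effect lasts. They are not: Table 5-4 also plans raw AFLS and its change from baseline, and the FACE-Q Appraisal of Lines score, in both TP and RP.
- **The zeros do not create a decline within TP.** A reader might infer that the tables would show a false loss of effect over time. Step 5 of the working shows otherwise: TP Month 1 against later TP visits is a like-for-like comparison, missing data aside.

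A reader might also take the 36% as the share of certain failures. It is a ceiling on everyone outside 2/2 or 3/3, many of whom may be able to respond.

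**Conclusion.** The point holds as a gap in the SAP's descriptive analyses. As written, the AFLS responder rates in TP and RP include participants who cannot respond. They are not comparable with the restricted Month 1 CP rate, and the VOLITE arm would carry two Month 1 AFLS figures. Counting the zeros can only lower the reported rate, so that error does not favour the device.

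The size is unknown because the documents give no count of baseline zeros. The range runs from no effect to a fall from 80% to 51.4%, with 77.1% and 65.7% at 10% and 50% of the up-to-75 subjects. These figures rest on the ceiling of 75 being reached, on the same proportions holding among treated participants, and on an 80% response in participants at 1, 4 or 2 with 3. The plan assumes 80% only for the restricted set.

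Nothing here supports a claim that the Month 1 AFLS test is compromised: its population, error rate and power are as planned.

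**What to change.** In SAP 5.5 and Table 5-4, state that AFLS responder status in TP and RP is summarised for VT and VRT participants with baseline AFLS of 2 on both cheeks or 3 on both, as SAP 5.4.2 already does for CP. If an all-treated responder table is also wanted, label it as additional and report how many participants have a baseline 0 on either cheek. Keep raw AFLS and change from baseline for all treated participants, as planned.

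The cost is a line of SAP text and a filter in the table programs. The downside is smaller denominators in these descriptive tables: about 94 to 96 of the 147 expected treated participants in TP before missing visits, and fewer in RP.

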5.6. Safety Analyses

The safety variables including AEs, injection site responses (ISRs), subject assessment of procedural pain, visual acuity, FACE-Q Recovery Early Life Impact questionnaire, confrontational visual fields, and ocular motility assessments will be analyzed using the safety population. Analyses of key safety variables for the Fitzpatrick safety cohort will be evaluated outside of the CSR analyses.

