5.1 Overall Design

[figure not shown]
This is a multicenter, evaluator-blind, controlled, parallel-design, prospective study of adults seeking improvement in cheek skin smoothness. Up to 20 investigational sites will enroll and follow subjects who meet the study criteria according to the study design in [Figure 5-1](#). Each site will have a PI who is responsible for the overall conduct of the study at that site and may also be the TI. The TI performs all study treatments, and the blinded EI evaluates ACSS, AFLS, and skin hydration measurements.

The study will span a total of approximately 20 months: an estimated 9 months for recruitment and 11 months for follow-up. For the treatment group, each subject's participation will encompass up to 30 days of treatment and up to 10 months of follow-up (6 months for those choosing not to receive repeat treatment at Month 6). For the control group, each subject's participation will encompass 1 month; for control subjects who opt to receive treatment, the treatment period will be up to 30 days, and the follow-up period will be up to 6 months.

Treatment group subjects receive initial treatment and optional touch-up treatment at 30 days if needed to achieve optimal correction. Follow-up visits are 3 days after each treatment (safety only) and at Months 1, 2, 4, and 6 after last treatment. Subjects exit the study at Month 6 or receive repeat treatment and are followed at Day 3 and Months 1 and 4 after repeat treatment. Control group subjects are followed for 1 month after randomization (no-treatment control period) and then either exit the study or receive optional treatment (initial and touch-up, if needed) in the delayed treatment period. Post-treatment follow-up visits are 3 days after each treatment and at Months 1, 2, 4, and 6 after last treatment.

To ensure adequate enrollment of subjects with Fitzpatrick skin phototype V and VI, up to 10 subjects may be enrolled in the Fitzpatrick V/VI safety cohort with less stringent inclusion criteria (see [Section 6.1](#)) and followed for safety only.

Figure 5-1 Study Design

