10.2 Populations for Analyses

The analysis populations will consist of subjects as defined below:

- The ITT population includes all randomized subjects. Subjects will be summarized as randomized.
- The safety population includes all subjects who are randomized to study treatment and receive at least 1 study treatment (treatment group) and subjects who are randomized to no treatment (control group). Subjects will be summarized as treated.

The Fitzpatrick V/V safety cohort will be included in the safety population for safety analyses and excluded from the ITT population for effectiveness analyses. All data for this cohort will be listed.

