10.3.1 Effectiveness Analyses

The effectiveness analyses will be based on the ITT population. All statistical tests will be 2-sided hypothesis tests performed at the 5% level of significance for main effects. All confidence intervals will be 2-sided 95% confidence intervals, unless stated otherwise.

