- The start and end of treatment periods listed above for the mis-treated participants (ie., randomized to Treatment and did not receive Volite or randomized to Control and was treated with Volite prior to the primary timepoint) will be determined based on the treatment received.
- For CP, effectiveness analyses and baseline characteristics will be performed on the mITT population using the “as-randomized” assignment.

JUVÉDERM VOLITE™ XC

- For TP, effectiveness and safety summaries will be performed on the VT population by treatment group.
- For RP, effectiveness and safety summaries will be performed on the VRT population.
- The baseline for applicable effectiveness endpoints and safety parameters will be the last non-missing assessment on or before the latter of randomization date or first treatment date in the control period
- The change from baseline values will be computed as the post-baseline value minus the baseline value.
- Continuous variables will be summarized by number of participants with observed values (n), mean, standard deviation (SD), median, 1st and 3rd quartiles (Q1, Q3), minimum (min), and maximum (max). Categorical variables will be summarized by the number of participants with observed values or events (n), frequency count (N1), and percentage of participants with observed values or events.
- All statistical hypothesis tests will be performed at the 2-sided 5% significance level, unless stated otherwise.
- In general, statistical analyses will be performed using SAS version 9.4 or higher. Adverse events (AEs) and medical history will be coded using the Medical Dictionary for Regulatory Activities (MedDRA) version 22.1 or higher.
- WHO Drug Dictionary will be used to code medications.

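### The SAP excludes the Fitzpatrick V/VI safety cohort from mITT but not from VT or VRT, so a safety-only cohort enters the treated-period and repeat-period effectiveness summaries

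*SAP*

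**What the plan says.** **Protocol.** Section 5.1 states that up to 10 subjects "may be enrolled in the Fitzpatrick V/VI safety cohort with less stringent inclusion criteria" and that their follow-up is for safety alone. Section 6 counts them within the randomization target for phototypes V/VI. Section 10.2 says the "safety cohort will be included in the safety population for safety analyses and excluded from the ITT population for effectiveness analyses", and adds: "All data for this cohort will be listed". Section 10.3.1 says: "The effectiveness analyses will be based on the ITT population". It makes no exception for later study periods.

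**SAP.** Section 1.2 repeats the safety-only purpose. In Section 4, Table 4-1, the mITT definition excludes the cohort by name. The VT definition does not. Its first limb is "Participants randomized and received VOLITE treatment at the beginning of the Control Period", and its second covers those given optional treatment after the control period. VRT is the part of VT that received repeat treatment, again with no exclusion. Section 5.1 then says: "For TP, effectiveness and safety summaries will be performed on the VT population by treatment group". It assigns VRT to the repeat period in the same way, and Section 5.5 confirms both sets for the other effectiveness endpoints.

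On safety, Section 5.6 first assigns the safety variables to the Safety population and then says: "Analyses of key safety variables for the Fitzpatrick safety cohort will be evaluated outside of the CSR analyses".

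**The concern.** Cohort members are randomized and can be treated, so they meet the VT definition and, if retreated, the VRT definition. A programmer following the SAP would include them in the treated-period and repeat-period summaries of ACSS, AFLS, FACE-Q, GAIS, natural look and feel, hydration and composite response.

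These are the only summaries that describe effect after Month 1 and after repeat treatment. The cohort differs from the main population by design. Under Table 4-1 a member has a baseline ACSS of 1 on a cheek, or unequal cheeks, or a converted FACE-Q score above 69. Two consequences follow:

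- **Composite threshold.** It is half the baseline standard deviation of the FACE-Q converted score (SAP 5.5), and the SAP does not say which set supplies that standard deviation. Protocol 6.1 caps the main population at 69. If VT supplies it, members above 69 could shift the cut-off for every subject.
- **Two Month 1 figures.** For the treatment group, several endpoints are summarized at Month 1 both in the control period (mITT) and in the treated period (VT). The two could differ because of the cohort, with no stated reason.

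**Working it through.** **Step 1. Trace the cohort through the SAP populations.**

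| Set | Cohort excluded? | Used for |
|---|---|---|
| mITT | Yes, by name | Control-period effectiveness, including the primary and both secondary comparisons |
| VT | No | Treated-period effectiveness and safety |
| VRT | No | Repeat-period effectiveness and safety |
| Safety | No | Control-period adverse events; named in SAP 5.6 for the safety variables |

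The primary, secondary and safety rows agree with Protocol 10.2. The effectiveness use of VT and VRT does not.

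**Step 2. Reproduce the plan's own figure.** The stated figure that depends on the number of treated subjects is the 95% power to detect a 2% adverse event in 147 treated (Protocol 10.1, SAP 3). The chance of at least one event is 1 − 0.98^147 = 0.949, which agrees. Excluding the cohort from effectiveness summaries leaves this figure unchanged. It would fall only if the cohort were also dropped from safety: 1 − 0.98^137 = 0.937.

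**Step 3. Size of the effect on a treated-period responder rate.** Inputs: 147 treated, being 119 + 28 (SAP 3); up to 10 in the cohort (Protocol 5.1); 80% assumed ACSS response at Month 1 (SAP 3). The documents give no cohort response rate, so the full 0% to 100% range is shown. The assumptions are that all 10 are treated, are among the 147, and have effectiveness data.

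- Share: 10/147 = 6.8%.
- No cohort responders: (137 × 0.80 + 0)/147 = 109.6/147 = 74.6%.
- All cohort members respond: (109.6 + 10)/147 = 81.4%.

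The shift is therefore −5.4 to +1.4 percentage points.

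**Step 4. Variations.**

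- *Fewer treated.* The plan expects 147 of 210 (70%) to be treated, or about 7 of 10 cohort members (7/147 = 4.8%). The range is then 140 × 0.80/147 = 76.2% to (112 + 7)/147 = 81.0%.
- *Within the treatment group.* The SAP reports by treatment group. With 7 of 119 in the cohort (5.9%), the range is 112 × 0.80/119 = 75.3% to (89.6 + 7)/119 = 81.2%. With all 10 in that group (8.4%), it is 109 × 0.80/119 = 73.3% to (87.2 + 10)/119 = 81.7%.
- *Later visit.* Take a 35% base rate, close to the 34.9% at Month 6 in study V12-001 (Protocol 3.2). The pooled range is 137 × 0.35/147 = 32.6% to (47.95 + 10)/147 = 39.4%.

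**The case against.** **The affected results are descriptive, and no hypothesis test changes.** This stands. The primary analysis and both secondary comparisons use mITT or a subset of it. The gap looks like an omission, since no SAP sentence deliberately adds the cohort.

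**The protocol leaves the other effectiveness analyses to the SAP (Protocol 10.3.1.1).** That allows the SAP to choose a treated set for later periods. It does not explain admitting the cohort, whose exclusion in Protocol 10.2 covers effectiveness analyses generally and whose safety-only purpose SAP 1.2 repeats.

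**Safety-only follow-up may mean that no post-baseline effectiveness data exist.** If so, the effect on observed-data summaries is nil. The documents do not settle this. The control-group visit tables (Protocol Tables 2-3 and 2-4) give the cohort no exemption from ACSS, AFLS or questionnaires.

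**The responder rules still work for these subjects.** This is correct. A score of 1 can fall to 0, and unequal cheeks can each improve by a point. The objection to including the cohort is that the protocol excludes it, and that does not depend on whether the endpoint can be computed.

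**A reader might infer from SAP 5.6 that the cohort's safety results leave the study report.** The documents do not support this. The preceding sentence uses the Safety population, which contains the cohort. SAP 5.6.3 summarizes adverse events on Safety, VT and VRT and lists them all. Because Table 4-1 names the cohort as its own population, the sentence most naturally means a separate cohort-only analysis. The protocol requires a listing of cohort data and no cohort-only table. Amendment 2 gives enrollment of phototypes V and VI as its reason, and Protocol 10.3.2 plans no safety summary by phototype.

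**Conclusion.** Wrong as written, on a limited point. Table 4-1 leaves the cohort in VT and VRT, and SAP 5.1 and 5.5 then carry it into effectiveness results, contrary to Protocol 10.2 and 10.3.1. At most 10 of about 147 treated subjects (6.8%) are involved. The possible pooled ACSS rate is 74.6% to 81.4% around an 80% base, if all 10 are treated and contribute effectiveness data. The shift within a reported group may differ.

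It would be tempting to conclude that the SAP reverses the protocol, admitting the cohort to effectiveness and removing it from safety. It does not. The cohort is out of the primary and secondary comparisons and in the pooled safety tables, as the protocol asks. The SAP 5.6 sentence is at most ambiguous. It would conflict with Protocol 10.2 only if read as taking cohort safety data out of the report.

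**What to change.** 1. In SAP 5.1 and 5.5, exclude the safety cohort from all effectiveness summaries on VT and VRT, and from the baseline FACE-Q standard deviation that sets the composite threshold.
2. State that the cohort stays in the Safety, VT and VRT safety summaries.
3. Reword the SAP 5.6 sentence so that it refers only to an additional cohort-only analysis, and say where that will be reported.
4. Confirm that all cohort data will be listed, as Protocol 10.2 requires.

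The cost is a few lines of SAP text and a population filter in the treated-period and repeat-period effectiveness programs. No new data are needed, and sample size and power do not change. A cohort-only table in the study report is optional.
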